5.5 Criteria for Removal from Study

In the absence of treatment delays due to adverse event(s), treatment may continue until one of the following criteria applies:

- Disease progression
- Intercurrent illness that prevents further administration of treatment \geq 14 days or specific changes in the patient's condition that render the patient unacceptable for further treatment in the judgment of the investigator
- Patient non-compliance with protocol requirements (determined via meeting with PI, applicable Sub-I, clinical research coordinator, and patient)
- Unacceptable adverse event(s). Note, a DLT in and of itself may not be an unacceptable adverse event. However, any grade 4 study-drug related AE is unacceptable and will lead to withdraw. The investigator will use his/her opinion, in consultation with the PI, to determine if a study-drug related AE is unacceptable, acceptable, or clinically insignificant (also acceptable).
- Withdrawal of consent (attempts should be made to clarify, with the patient, if withdrawal is specific to study participation, or if it applies to data collection as well). Note: patients lost to follow up (defined as no contact $>$ 60 days after last on-study contact and at least 3 attempts) are considered to have withdrawn study participation consent. Data collection is permissible. Date of last contact will be recorded as the withdrawal date.
- Pregnancy
- Oncoceutics' decision to forgo further drug development of ONC201

The reason for study removal and the date the patient was removed must be documented in the CRF.

Severe adverse events, availability of new adverse toxicology in animals, and financial difficulties due to withdrawal of funds may result in stopping the trial. An investigator, Sponsor, or IRB may take such actions. If the trial is terminated for safety reasons, subjects will be notified immediately and assured that appropriate treatment and follow-up will be available. If an investigator terminates the trial he will inform the Sponsor, subjects, and IRB about the reason for such action. Similarly if the Sponsor terminates the trial, it will inform the investigators, the IRB, and the subjects of the reason for such an action. Similar notifications will be sent by the IRB if it takes such an action.

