6 DOSING DELAYS/DOSE MODIFICATIONS

The descriptions and grading scales found in the revised NCI Common Terminology Criteria for Adverse Events (CTCAE) version 4.0 will be utilized for dose delays and dose modifications.

Below are dose modifications (Table 6.1) for adverse events that are attributable to study drug, including: nausea, vomiting, diarrhea, neutropenia, and thrombocytopenia. If a patient

experiences other adverse events, or several adverse events and there are conflicting recommendations based on Grade, the investigator will use the recommended dose adjustment that reduces the dose. Dose modifications will be made based on an adverse event that occurs during any time during a cycle.

Criteria for disrupting treatment, dose modification, or discontinuation are listed in Table 6.1. Dose modifications are per the clinical judgment of the investigator and agreement of the subject, the treatment will be resumed according to the table below. Dose modification may not be required for adverse events that are clinically manageable.

Table 6.1 Dose adjustment rules for Adverse Events (AEs), including Nausea, Diarrhea, Neutropenia, Thrombocytopenia, and Other AEs. Alopecia does not require dose adjustments.

CTCAE Grade	Management/Next Dose for ONC201
≤ Grade 2	No change in dose
Grade 3 or 4*	Hold until < Grade 2. For first instance, if resolved to < Grade 2 within 21 days resume dosing at 500mg ONC201 and 8mg dexamethasone. For second instance, if resolved to < Grade 2 within 21 days resume dosing at 8mg dexamethasone and 375mg ONC201.**

*Patients requiring a delay of >21 days weeks should go off protocol therapy.

**Patients requiring > two dose reductions should go off protocol therapy.

Participants who experience an adverse event that requires a treatment delay or dose reduction should be monitored with appropriate laboratory testing or other clinical evaluation at least weekly until resolution; if the adverse event does not resolve within 21 days, the interval for testing may be reduced after consultation and written approval by the Overall Principal Investigator (or his designee).

For holds for reasons other than treatment related toxicities, if the participant does not meet criteria to resume treatment within 6 weeks of the event precipitating the hold, the study

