7 STUDY PROCEDURES

Note that hematology, blood chemistry, and urinalysis, below, refers to any biologic sampling done for safety or efficacy testing, as detailed in the Schedule of Activities. For example, patients with multiple myeloma may undergo a 24-hour urine collection but this is not explicitly defined in the text below. The Schedule of Activities take precedence over text in this section.

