	# responders (inclusive)
1-11	Never stop with this many patients
12-23	0
24-25	0-1
26	Reach maximum number of patients, always stop

10.3 Early Stopping Rules for Safety/adverse events:

Adverse events will be assessed continuously throughout the study. During evaluation of the first cohort of 12 eligible patients, if 4 patients have to discontinue the study drug due to treatment-related adverse events, the study will be interrupted for consideration of dose reduction or termination. If 6 of a total of 26 eligible patients have to discontinue the study drug due to treatment-related adverse events the study will be suspended and early termination for excess toxicity will be considered after careful investigation of the causes of the higher than expected toxicities. Once the cause of the higher than anticipated toxicities has been determined, the study team will confer with the FCCC DSMC and IRB to make a determination whether accrual can be resumed or the study will be terminated early. The chance of early termination with a true toxicity of 30% is 51%. The chance of early termination in error (when true toxicity is 5%) is 0.2%. The overall study power is 85% (for detection of overly toxic treatment) and has type I error of 0.3%.

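### Table 6.1 re-doses patients after a drug-related grade 4 event that Sections 5.5 and 7.6 say must end treatment, and its fixed 500 mg re-start exceeds the 375 mg Phase 1 starting dose

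*Combined protocol and SAP*

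**What the plan says.** Section 6 introduces its dosing table with these words: "Below are dose modifications (Table 6.1) for adverse events that are attributable to study drug". The table has one row for grades 3 and 4 together. Treatment is held until the event is below grade 2. If that happens within 21 days, the instruction is: "For first instance, if resolved to < Grade 2 within 21 days resume dosing at 500mg ONC201 and 8mg dexamethasone". After a second such event the re-start is 375 mg ONC201 with 8 mg dexamethasone. Footnotes take a patient off therapy if the delay exceeds 21 days or more than two reductions are needed. The surrounding text leaves modifications to the investigator's judgment and the patient's agreement, but that same sentence ends: "the treatment will be resumed according to the table below". It is followed by: "Dose modification may not be required for adverse events that are clinically manageable".

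Section 5.5, repeated in Section 7.6, allows that a DLT need not end treatment but then states that "any grade 4 study-drug related AE is unacceptable and will lead to withdraw".

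Section 3.3 starts Phase 1 at 375 mg ONC201 with 20 mg dexamethasone and escalates to 625 mg. If the first cohort is too toxic, it steps down to 375 mg with 8 mg dexamethasone and then lower in 125 mg decrements. The synopsis and Sections 5.2 and 7.3 describe 625 mg without mentioning the 375 mg start.

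Section 10.3 counts discontinuations for treatment-related events: "if 4 patients have to discontinue the study drug due to treatment-related adverse events, the study will be interrupted".

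**The concern.** There are two faults, and the first carries the weight.

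**Grade 4 events.** The same event (drug-related, grade 4, back below grade 2 within 21 days) is re-dosed under Table 6.1 and ends treatment under Sections 5.5 and 7.6. This concerns what happens to a patient after a life-threatening drug reaction, and it applies at every dose in both phases. The rule a site follows also decides whether that patient counts towards the Section 10.3 safety boundary.

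**Fixed re-start doses.** The table's footnote treats its steps as reductions, but for ONC201 they are reductions only from 625 mg. A patient in the 375 mg starting cohort who followed the table would receive more ONC201 after a grade 3 or 4 attributable toxicity.

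**Working it through.** **1. Can the two grade 4 rules be reconciled?**

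| Drug-related grade 4 event | Table 6.1 | Sections 5.5 and 7.6 |
|---|---|---|
| Below grade 2 within 21 days, first time | Resume at 500 mg + 8 mg | Withdraw |
| Below grade 2 within 21 days, second time | Resume at 375 mg + 8 mg | Withdraw |
| Delay over 21 days | Off therapy | Withdraw |
| More than two reductions needed | Off therapy | Withdraw |

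The rules agree only in the last two rows. Possible ways to reconcile the first two:

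- *Reserve the grade 4 row for unrelated events.* The table title does extend to other adverse events, so the row could serve them. The introduction, however, makes attributable events the table's subject and names neutropenia and thrombocytopenia. Section 6 also has a separate 6-week provision for holds not caused by treatment-related toxicity.
- *Let Section 5.5 govern discontinuation and Section 6 govern dose only.* Section 6 says that Table 6.1 also holds the discontinuation criteria, so both sections claim the decision.
- *Apply the Section 6 tie-break.* It chooses between conflicting grade-based dose adjustments, not between re-dosing and withdrawal.
- *Apply a precedence clause.* The only one found is in Section 7: "The Schedule of Activities take precedence over text in this section". It ranks the schedule over Section 7 text, and the schedule has no re-dosing or withdrawal rule.

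A concrete case is related grade 4 neutropenia lasting 7 days or less. Section 5.6 does not make it a DLT (that needs more than 7 days). Table 6.1 re-doses the patient once it resolves; Sections 5.5 and 7.6 withdraw the patient.

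**2. Re-start dose against assigned dose**

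Inputs are the assigned doses in Section 3.3 and the re-start doses in Table 6.1. Change = re-start dose / assigned dose − 1.

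| Assigned ONC201 | First re-start, 500 mg | Second re-start, 375 mg |
|---|---|---|
| 625 mg | 500/625 = 0.80 (−20%) | 375/625 = 0.60 (−40%) |
| 375 mg | 500/375 = 1.33 (+33%) | 375/375 = 1.00 (no change) |
| 250 mg (only if de-escalated) | 500/250 = 2 times | 375/250 = 1.5 times |
| 125 mg (only if de-escalated) | 500/125 = 4 times | 375/125 = 3 times |

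Dexamethasone falls from 20 mg to 8 mg (8/20 = 0.40, −60%) in the planned cohorts and is unchanged in any cohort already on 8 mg.

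**3. Side effect on the Section 10.3 boundary**

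Let p be the probability that a patient discontinues for a treatment-related event.

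- First boundary: P(X₁₂ ≥ 4), with X₁₂ ~ Bin(12, p).
- Either boundary: P(X₁₂ ≥ 4) + Σ over x = 0 to 3 of P(X₁₂ = x) · P(Y ≥ 6 − x), with Y ~ Bin(14, p) for the remaining 26 − 12 = 14 patients.

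| p | 4 of 12 | Either boundary |
|---|---|---|
| 5% | 0.0022 | 0.0033 |
| 10% | 0.0256 | 0.0532 |
| 30% | 0.507 | 0.849 |

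The 5% and 30% rows reproduce the plan's own figures: 0.2% and 51% for the first boundary, 0.3% and 85% overall. One of these is stated as "The chance of early termination in error (when true toxicity is 5%) is 0.2" per cent.

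The 10% row is the plan's 5% plus an assumed 5 points for patients withdrawn rather than re-dosed. If 0 to 5 further points of patients are affected, the 4-of-12 trigger probability lies between 0.2% and 2.6%, and the either-boundary probability between 0.3% and 5.3%. The documents do not give the true share.

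**The case against.** The best reply is that the two grade 4 rules are not equally open. The withdrawal rule is categorical and stated twice, while Table 6.1 is subject to investigator judgment. A site that withdraws the patient can claim to satisfy both texts; a site that re-doses breaches Section 5.5. On this reading, Section 5.5 decides who remains on study and the table doses those who remain. That makes withdrawal the safer reading. It does not make the table consistent: its row still names grade 4, its scope is attributable events, and the sentence granting judgment sends the investigator back to the table to resume.

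A second reply is that such events may be rare. Section 1.3 reports no drug-related toxicity above grade 1 in ten evaluable patients dosed every three weeks, and no drug-related adverse events in nine patients dosed weekly. This is fair evidence on reach, but the numbers are small and the drug was given without dexamethasone, so they do not settle the rate here.

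Third, the 10% rate in the Section 10.3 calculation is an assumption and the movement is modest. That stands, and the boundary effect is secondary.

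Fourth, nobody would deliberately raise the dose after toxicity, and investigator discretion makes it unlikely. That also stands. It limits the practical harm of the 375 mg problem but does not correct the table.

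Finally, defaulting to withdrawal is a choice. Short grade 4 neutropenia is not a DLT, and Section 6.1.5 allows G-CSF for grade 4 neutropenia lasting more than 7 days, so a sponsor might reasonably prefer to re-dose some of these patients. The fix should leave that option open.

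**Conclusion.** Both rules are wrong as written and need correction. The grade 4 conflict is the reason this is a must-fix. It gives opposite instructions for every drug-related grade 4 event that falls below grade 2 within 21 days, at every dose and in both phases, and no text resolves it. The documents do not show which side is the error, and they give no frequency for such events on the combination.

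The re-start dose problem is certain on the text but narrow: +33% ONC201 at the first re-start from 375 mg, and no reduction at the second. It affects the 375 mg starting cohort, about 3 to 6 of the up to 12 Phase 1 patients if the cohort has the usual 3+3 size (assumption), and only those with an attributable grade 3 or 4 event. The lower-dose cohorts are affected only if de-escalation occurs. At 625 mg the table works as intended.

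No effect on the primary endpoint's power or alpha is shown.

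**What to change.** - **One grade 4 rule.** By default, limit the Table 6.1 re-dosing row to grade 3 for drug-related events, which matches Sections 5.5 and 7.6. If the sponsor wants to re-dose after some grade 4 events, such as short neutropenia, amend Sections 5.5 and 7.6 to list them.
- **Relative re-start doses.** Define each re-start as a step below the dose at which the event occurred and never above it. Steps of 125 mg fit, being both the table's own step size (625 to 500 to 375 mg) and the capsule strength in Section 5.1.1. Take the patient off therapy if no lower level exists.
- **Floor.** Confirm whether the 125 mg + 8 mg minimum in Section 3.3, written for cohort de-escalation, also applies within a patient.
- **Root cause.** Make the synopsis and Sections 5.2 and 7.3 refer to the assigned dose level instead of 625 mg.

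The cost is amendment wording, with no change to planned sample size, visits or data collection. One consequence to note: Section 10.1 requires two cycles for evaluability and Section 3.2 counts evaluable Phase 2 patients, so patients withdrawn early may need replacing. The present Sections 5.5 and 7.6 already carry that consequence.

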6.1 Concomitant Medications

6.1.1 Drug Interactions

No formal metabolic or drug-drug interactions with ONC201 or any metabolites have been performed. These studies will be performed later in the development of this agent. A literature search revealed that ONC201 was inactive in a CYP450 screen. Strong inducers and inhibitors of the cytochrome P450 system should not be used on study. Concomitant medications that have risk of Torsades de Pointes are also not allowed.

6.1.2 Corticosteroids

Dexamethasone will be given to all patients per study protocol. Additional steroids will be restricted to physiologic replacement or less for those in which it is clinically indicated.

Use of non-systemic steroid use is permitted (e.g. cream, lotion, inhalers).

6.1.3 Anti-emetic Therapy

There are no restrictions on use of antiemetic therapy for this trial. Premedications to prevent emerging toxicities are permitted as long as their use does not conflict with other guidelines in this protocol.

6.1.4 Other Anticancer or Experimental Drugs

Treatment with other anticancer or experimental drugs is not permitted for patients treated on this protocol. Exceptions include use of LHRH, and octreotide.

6.1.5 Hematopoietic Growth Factors

The use of any growth factor is not permitted for patients during the DLT window, unless it's use is deemed medically necessary by the treating physician secondary to an emerging toxicity. In this situation, only G-CSF is permitted for neutropenic fever or grade 4 neutropenia > 7 days duration, if the investigator feels such treatment would be in the patient's best interest. Use of growth factors outside of the DLT window must follow institutional and ASCO guidelines. In situations where G-CSF is felt to be warranted, pegylated G-CSF should only be used if the study drug dosing interval is 2 weeks or greater. G-CSF must be used if the study drug dosing interval is 1 week.

The use of erythropoietin growth factor is generally discouraged. Use of erythropoietin must follow institutional and ASCO guidelines. The use of a thrombopoietin agonist is not permitted.

6.2 Palliative and Supportive Care

All palliative care necessary for optimal care of the patient should be provided. Investigational drug must be held during radiotherapy and for 1 week afterwards. If possible, the investigational drug should be held for 1 week prior to the administration of palliative radiotherapy if possible. It is not known if ONC201 acts as a radiosensitizer or if this would lead to increased toxicity.

However, the potential for ONC201 to act as a radiosensitizer exists. ONC201 should be held for at least one week prior to any elective surgery.

7 STUDY PROCEDURES

Note that hematology, blood chemistry, and urinalysis, below, refers to any biologic sampling done for safety or efficacy testing, as detailed in the Schedule of Activities. For example, patients with multiple myeloma may undergo a 24-hour urine collection but this is not explicitly defined in the text below. The Schedule of Activities take precedence over text in this section.

7.1 Baseline

The following procedures/assessments must be performed within 28 days prior to the first dose of ONC201.

- Patient signature on informed consent form
- Medical history, including tumor history, history of other disease processes (active or resolved), concomitant illnesses, and demographics.
- Tumor assessment.

The following procedures/assessments must be performed within 28 days prior to the first dose of ONC201.

- Baseline signs and symptoms
- Vital signs
- Height
- Weight
- Physical exam
- ECOG performance status
- Hematology, blood chemistry, coagulation, urinalysis and per SoA
- Pregnancy test (serum or urine), if applicable
- TriPLICATE EKG (12 leads)
- Concomitant medications

Following successful completion of the baseline assessments and confirmation of eligibility patients may be enrolled.

7.2 Trials Period

The following procedures/assessments will be performed on the days specified in the Schedule of Activities:

- Vital signs
- Weight
- ECOG performance status
- Physical exam
- Hematology, blood chemistry, coagulation, urinalysis, and per SoA
- Triplicate EKG (12 leads)
- Study drug compliance
- Adverse events
- Drug compliance
- Concomitant medications
- Tumor assessment: at the end of every even cycle (e.g., Cycles 2, 4, 6)
- Blood draws for PK/PD
- Urine collection

7.3 Treatment

ONC201 will be orally administered at 625mg weekly day 1, day 8, and day 15 of each treatment cycle (21 days). Dexamethasone will be administered at the indicated dose on each day that ONC201 is administered in each treatment cycle (day 1, day 8, and day 15). Administration of dexamethasone is recommended approximately 6 hours (+ 2 hours) after ONC201.

7.4 End of Treatment Visit

A final visit ("Follow Up") will occur for all patients when disease progression is documented or subsequent anticancer therapy is initiated or the patient is withdrawn from treatment for any other reason.

The following procedures/assessments will be carried out as described in the Schedule of Activities table and unless performed in the previous week. Every effort should be made to have a final tumor assessment.

- Vital signs
- Weight
- ECOG performance status
- Triplicate EKG (12 leads)
- Hematology, blood chemistry, coagulation, urinalysis and per SoA
- Tumor assessment, unless carried out in the previous 6 weeks
- Adverse events
- Concomitant medications

7.5 Follow-up Visit

Safety follow up will continue in all patients for 28 days after the last dose of treatment. For those patients who have discontinued study treatment for reasons other than disease progression, all tumor assessments should be repeated every 6 weeks until disease progression or another antitumor therapy is initiated.

7.6 Patient Withdrawal

In the absence of treatment delays due to adverse event(s), treatment may continue until one of the following criteria applies:

- Disease progression
- Intercurrent illness that prevents further administration of treatment \geq 14 days or specific changes in the patient's condition that render the patient unacceptable for further treatment in the judgment of the investigator
- Patient non-compliance with protocol requirements (determined via meeting with PI, applicable Sub-I, clinical research coordinator, and patient)
- Unacceptable adverse event(s). Note, a DLT in and of itself may not be an unacceptable adverse event. However, any grade 4 study-drug related AE is unacceptable and will lead to withdraw. The investigator will use his/her opinion, in consultation with the PI, to determine if a study-drug related AE is unacceptable, acceptable, or clinically insignificant (also acceptable).
- Withdrawal of consent (attempts should be made to clarify, with the patient, if withdrawal is specific to study participation, or if it applies to data collection as well). Note: patients lost to follow up (defined as no contact $>$ 60 days after last on-study contact and at least 3 attempts) are considered to have withdrawn study participation consent. Data collection is permissible. Date of last contact will be recorded as the withdrawal date.
- Pregnancy
- Oncoceutics' decision to forgo further drug development of ONC201

8 ASSESSMENTS

8.1 Safety Evaluations

Safety assessments include collection of AEs, SAEs, and safety laboratory. Assessment of adverse events will include the type, incidence, severity (graded by the National Cancer Institute Common Terminology Criteria for Adverse Events [NCI CTCAE] version 4.03), timing, seriousness, and relatedness.

Baseline signs and symptoms will be recorded at baseline and then reported as adverse events during the trial if they worsen in severity or increase in frequency.

The minimum requested lab data includes:

Table 7.1: Laboratory Tests Required (All patients)

Hematology	Blood Chemistry	Urinalysis	Coagulation tests
White Blood Cell Count (WBC)	Glucose	pH	Activated partial thromboplastin time (APTT)
Absolute Neutrophil Count (ANC)	BUN	Specific gravity	Prothrombin time
Platelet count	Creatinine	Protein	
Hemoglobin	Albumin	Glucose	
WBC differential count	AST/ALT	Ketones	
	Total Bilirubin	Blood	
	Alkaline phosphatase	Leukocyte esterase	
	LDH	Nitrates	
	Sodium		
	Magnesium		
	Potassium		
	Calcium		
	Phosphate		
	Uric Acid		

Investigators may order additional blood tests for planning treatment administrations, dose modification, or further evaluation of adverse events.

Additional assessments are defined in the Schedule of Activities table.

